10.3.1.1. Columbia-Suicide Severity Rating Scale (C-SSRS)

The C-SSRS is a clinician-administered interview developed by researchers at Columbia University to assess suicide risk and to track suicidal ideation and behavior during clinical trials. This scale is intended to be administered by individuals who have received training in its administration. The questions contained in the Columbia-Suicide Severity Rating Scale are suggested probes. Ultimately, the determination of the presence of suicidal ideation or behavior depends on the judgment of the individual administering the scale.

The “since last visit” version of the C-SSRS will be completed at all study visits. Note that if there has been a significant change in responses to this scale indicative of increased suicide risk, appropriate intervention should be prescribed [Section 10.3.1.2](#) and an AE should be recorded.

10.3.1.2. Safety Planning Intervention (SPI)

The C-SSRS is completed at every visit in order to assess for changes in suicidality during the study. If a patient scores a 4 or 5 on the Suicidal Ideation section of the C-SSRS at a clinic visit following enrollment, the patient should be withdrawn from the study and referred for appropriate emergency care. A score of 4 or 5 should also result in the reporting of a serious adverse event.

If a patient scores a 2 or 3 on the Suicidal Ideation section of the C-SSRS at any visit, the investigator should consider the implementation of a Safety Planning Intervention (SPI). The recommended SPI for this study is the plan developed by [name] and [name] which has been adopted by the U.S. Veteran’s Administration (VA) ([Stanley & Brown, 2012](#)). The VA SPI is a brief clinical intervention aimed at mitigating suicide risk. It consists of a written, prioritized list of coping strategies and sources of support that patients can use to alleviate a suicidal crisis. Sites may use an internally-developed SPI if similar in scope and purpose to the VA SPI.

10.3.1.3. Visual Examination of Oral Cavity

A visual examination of the oral cavity should be done at Baseline (Visit 1) and after 12 weeks (Visit 5) of treatment and/or at Early Termination. In addition to these regularly scheduled examinations, a visual inspection of the oral cavity (including the sublingual area) should be done any time a patient reports an oral adverse event (other than numbness, tingling or bitter taste) in order to document presence or absence of any visible abnormalities. Additional details related to onset, duration, severity and reversibility of oral events will also be documented in the CRF.

10.3.1.4. Vital Signs

Vital signs (sitting blood pressure and heart rate, respiratory rate, oral temperature, and weight) will be assessed at Visits 1, 3, 4 and 5. Height will be transferred from the lead-in study database, and BMI for the P303 baseline and Visit 5 will be calculated using height from the lead-in study baseline and weights from P303 baseline and Visit 5, respectively.

10.3.1.5. Clinical Laboratory Assessments

The clinical laboratory evaluations to be performed in this study are listed in [Table 2](#). All tests will be performed at Baseline (Visit 1) and after 12 weeks of treatment (Visit 5), or Early Termination.

With the exception of the urine pregnancy tests, all clinical laboratory evaluations will be analyzed via a central clinical laboratory, and information regarding appropriate sample volume, collection tubes, sample labeling and handling, and shipment will be provided in a study manual. Each clinically significant abnormal laboratory value or other clinically meaningful abnormality should be followed until the abnormality resolves or until a decision is made that it is not likely to resolve. If such abnormalities do not return to normal within a reasonable period, their etiology should be identified and Tonix or designee should be notified. Treatment-emergent clinically significant abnormalities in laboratory values will be recorded as AEs.

Table 2: Clinical Laboratory Assessments

Clinical chemistry	Hematology
Alanine aminotransferase (ALT)	Hematocrit
Alkaline phosphatase	Hemoglobin
Aspartate aminotransferase (AST)	MCH concentration (MCHC)
Bilirubin (total)	Mean corpuscular hemoglobin (MCH)
Blood urea nitrogen (BUN)	Mean corpuscular volume (MCV)
Calcium	Platelet count
Chloride	Red blood cell (RBC) count
Cholesterol (total)	WBC differential
Creatine kinase (CK)	Neutrophil count (absolute and %)
Creatinine	Lymphocyte count (absolute and %)
Glucose	Monocyte count (absolute and %)
Phosphorus	Eosinophil count (absolute and %)
Potassium	Basophil count (absolute and %)
Protein (albumin and total)	White blood cell (WBC) count
Sodium	
Urine Pregnancy Test (qualitative dipstick) ^a	

^a Pregnancy testing for females of child-bearing potential only. A positive pregnancy test mandates withdrawal from the study (all visits).

11. DEFINITIONS, RECORDING, AND REPORTING OF ADVERSE EVENTS AND PREGNANCY

11.1. Definition of Adverse Events

According to International Conference on Harmonisation (ICH) guidance E2A, Clinical Safety Data Management: Definitions and Standards for Expedited Reporting, an adverse event (AE) is any untoward medical occurrence in a patient or clinical investigation patient administered a pharmaceutical product and which is not necessarily required to have a causal relationship with this treatment. An AE can therefore be any unfavorable and unintended sign (including an abnormal laboratory finding, for example), symptom, or disease temporally associated with the use of a medicinal product, whether or not considered related to the medicinal product.

A newly-emergent adverse event (NEAE) is defined as any new AE that starts after the patient's baseline visit for P303, or any ongoing AE that was first reported during the lead-in study and which then exhibits an increase in severity, frequency or relationship after the patient's participation in P303 has begun. NEAEs and "All AEs" will be tallied by SOCs and preferred terms. Adverse events that are ongoing at the time of the patient's baseline visit for P303 but which resolve, or persist without change in severity, frequency or relationship to study drug during the extension study, will be included in the tally of All AEs.

11.2. Adverse Event Recording

11.2.1. Coding the Adverse Event

Standard medical terminology should be used in describing AEs. MedDRA® will be used as the standard coding dictionary for AEs and in describing the patient's medical history, and the World Health Organization (WHO) Drug Dictionary will be used to code concomitant medications. Informal descriptions should be avoided.

11.2.2. Severity of Adverse Event

AEs should be graded as mild, moderate, or severe using the following definitions.

- **Mild:** Awareness of signs or symptoms, but easily tolerated and of minor irritant type causing no loss of time from normal activities. Symptoms do not require therapy or a medical evaluation; signs and symptoms are transient.
- **Moderate:** Events introduce a low level of inconvenience or concern to the participant and may interfere with daily activities, but are usually improved by simple therapeutic measures; moderate experiences may cause some interference with functioning.
- **Severe:** Events interrupt the participant's normal daily activities and generally require systemic drug therapy or other treatment; they are usually incapacitating.

To make sure there is no confusion or misunderstanding of the difference between the terms "serious" and "severe," which are not synonymous, the following note of clarification is provided. The term "severe" is often used to describe the intensity (severity) of a specific event (as in mild, moderate, or severe myocardial infarction); the event itself, however, maybe of

relatively minor medical significance (such as severe headache). This is not the same as “serious,” which is based on patient/event outcome or action criteria usually associated with events that pose a threat to a patient’s life or functioning. Seriousness (not severity) serves as a guide for defining regulatory reporting obligations.

11.2.3. Relationship of Adverse Events to Study Drug

The investigator will assess the potential relationship of the AE to study drug using the following descriptions.

- ***Not Related:*** This category applies to an AE that is clearly not related to the investigational agent/procedure, beyond a reasonable doubt. That is, another cause of the event is most plausible; and/or a clinically plausible temporal sequence is inconsistent with the onset of the event and the administration of study drug and/or a causal relationship is considered biologically implausible.
- ***Unlikely Related:*** This category applies to an AE that could reasonably be considered caused by something else, and where there is no known or expected response pattern to the suspected study drug.
- ***Possibly Related:*** This category applies to an AE that follows a reasonable temporal sequence from administration of the study drug and that follows a known or expected response pattern to the suspected study drug, but that could readily have been produced by a number of other factors.

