5. TRIAL OBJECTIVES AND PURPOSE

5.1. Primary Objective

The primary objective of the study is to evaluate the safety of TNX-102 SL taken daily at bedtime over an additional 12 weeks in patients with PTSD who have completed a double-blind lead-in study.

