7.3.1 Adverse Event and Prior/Concomitant Medication handling conventions

To handle missing or partial AE and prior/concomitant medication dates, the following rules will be applied.

For partial start dates:

1. If the year is unknown, then do not impute the date but assign a missing value.
2. If the month is unknown, then:
 - a. If the year matches the year of the first dose date, then impute the month and day of the first dose date.
 - b. Otherwise, assign “January.”
3. If the day is unknown, then:
 - a. If the month and year match the month and year of the first dose date, then impute the day of the first dose date.
 - b. Otherwise, assign “01.”

For partial end dates:

1. If the year is unknown, then do not impute the date but assign a missing value.
2. If the month is unknown, then assign “December.”
3. If the day is unknown, then assign the last day of the month.

After implementing the rules above, to determine whether medications with missing start or stop dates are prior or concomitant medications, the following strategy will be used:

1. If the start date and stop date are both missing, then the most conservative approach is taken and the medication is considered to be a concomitant medication.
2. If the start date is missing but the stop date is not missing and is after the day of first study dose administration, then the most conservative approach is taken and the medication is considered to be concomitant.
3. If the start date is missing but the stop date is not missing and is on or before the day of first study dose and after the date of signed informed consent, then the medication is considered to be a prior medication.
4. If the start date is not missing but the stop date is missing, then the most conservative approach is taken and medication is considered to be concomitant.

The missing severity of an AE will be imputed to “severe”; the missing relationship to study drug of an AE will be imputed to “related”.

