10.1 Adverse Events

All AEs, newly-emergent adverse events (NEAEs), and SAEs will be coded using MedDRA, version 19.0.

Newly emergent adverse events (NEAEs) are defined as any new AE that started after the patient's first dose of P303 study drug, or any unresolved AE first reported in P301 that exhibited an increase in severity, frequency or relationship after the patient's participation in P303 had begun.

An AE summary table will be presented for the following:

- NEAEs by severity
- NEAEs leading to study drug discontinuation
- NEAEs by relationship
- SAEs
- Oral Cavity NEAEs
- All AEs (including both NEAEs and ongoing AEs from the lead-in study)
- All Oral Cavity AEs (including both Oral Cavity NEAEs and ongoing Oral Cavity AEs from the lead-in study)

Summaries of incidence rates (frequencies and percentages) of individual AEs by MedDRA SOC and preferred term will be prepared. Such summaries will be displayed for all NEAEs, NEAEs by maximum severity, NEAEs by strongest relationship to study drug, oral cavity NEAEs, all AEs (including both NEAEs and ongoing AEs from the lead-in study), and all oral cavity AEs (including both oral cavity NEAEs and ongoing oral cavity NEAEs from the lead-in study).

Each participant will be counted only once within each summation level (SOC; preferred term). If a participant experiences more than one NEAE within each summation level only, the NEAE with the strongest relationship or the maximum severity, as appropriate, will be included in the summaries of relationship and severity.

Additionally, a summary of the Oral Cavity AE characteristics will be presented; this includes information such as temporal proximity to the dose, duration and whether the AE was present the following morning.

Adverse events of special interest pertaining to abuse potential will be analyzed separately by treatment group, SOC and preferred term, and displayed in tabular format. Terms to be included may be found in [Appendix 3](#).

In the AE data listings, all AEs will be displayed. A separate by-patient listing of oral cavity AEs (including oral cavity AEs that were ongoing from P301) will be provided. AEs that are newly-emergent will be flagged in all AE listings.

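### The protocol's three causality categories do not cover every event: a well-timed event of a type not yet known for the drug cannot be rated 'Possibly Related', and the SAP imputes a value outside the scale

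*Protocol*

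**What the plan says.** Protocol 11.2.3 tells the investigator to assess relationship with three descriptions.

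- **Not Related**: the event is "clearly not related to the investigational agent/procedure, beyond a reasonable doubt". This is explained as another cause being most plausible, and/or timing that does not fit, and/or a causal link that is biologically implausible.
- **Unlikely Related**: the event "could reasonably be considered caused by something else, and where there is no known or expected response pattern to the suspected study drug". Both parts must hold.
- **Possibly Related**: the timing after dosing must be reasonable, and the event must be one which "follows a known or expected response pattern to the suspected study drug, but that could readily have been produced by a number of other factors".

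There is no Probably, Definitely or plain Related category. SAP 10.1 adds no other scale. It plans summaries of NEAEs by relationship and, by system organ class and preferred term, "NEAEs by strongest relationship to study drug". SAP 7.3.1 states that "the missing relationship to study drug of an AE will be imputed to" the value 'related'.

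Protocol 11.1 and SAP 10.1 also use the rating in defining an NEAE. An event ongoing from the lead-in becomes newly emergent if its severity, frequency or relationship increases during P303.

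**The concern.** The highest rating is open only to events that look like something the drug is already known or expected to do and that also have ready competing explanations. Absence of a known pattern is, in turn, part of the definition of Unlikely Related. An unfamiliar reaction is therefore barred from the top category, and a clear drug effect with nothing else to explain it has no category.

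This matters because safety is the purpose of the study: "The primary objective of the study is to evaluate the safety of TNX-102 SL taken daily at bedtime over an additional 12 weeks". Protocol 6.1 foresees continuous exposure of up to about 24 weeks. The appended package insert is for an oral product not recommended beyond 2 or 3 weeks. Effects of the sublingual route or of longer use are among those least likely to be known already. Protocol 8.5 relaxes the lead-in's medication restrictions, so another reasonable cause will often be arguable. At stake is whether the relationship tables mean what their labels suggest.

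**Working it through.** The plan gives no figure to reproduce. The check sets the three definitions against each combination of three yes/no features: reasonable timing, known or expected pattern, and plausible other cause. 'Reasonably' caused by something else (Unlikely Related) and 'readily' produced by other factors (Possibly Related) are treated as one feature, which is a simplification.

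Conditions from Protocol 11.2.3:

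- Possibly Related = timing AND known pattern AND other cause.
- Unlikely Related = other cause AND no known pattern.
- Not Related = timing inconsistent. Its two other routes are taken up below the table.

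| Timing reasonable | Known or expected pattern | Other cause | Category as written |
|---|---|---|---|
| yes | yes | yes | Possibly Related |
| yes | yes | no | none |
| yes | no | yes | Unlikely Related |
| yes | no | no | none |
| no | yes | yes | Not Related |
| no | yes | no | Not Related |
| no | no | yes | Not Related and Unlikely Related |
| no | no | no | Not Related |

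Of the four well-timed combinations, 2 of 4 have no category, and both are those without a competing cause. In 0 of the 2 well-timed combinations without a known pattern can the event be rated Possibly Related. One combination with inconsistent timing meets two categories.

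The other routes into Not Related do not close the gaps. 'Another cause most plausible' cannot apply where there is no other cause. 'Biologically implausible' does not describe a suspected drug effect.

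**Example.** Protocol 10.3.1 and SAP 10.5 treat numbness, tingling and bitter taste as familiar sensory effects. Numbness right after dosing with no other explanation is the second row: known pattern, good timing, no category.

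**Lenient reading.** Suppose the other-factors clause is a concession and not a requirement. The second row then becomes Possibly Related, leaving 1 of 4 well-timed combinations without a category. The two rows without a known pattern do not change.

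**Missing values.** The scale's values are Not, Unlikely and Possibly Related. The imputed value 'related' is none of these, and the SAP does not say where it ranks when the strongest relationship is chosen. If it ranks highest, as its name suggests, a missing rating outranks any rating an investigator can record.

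**Where the category enters the analysis.**

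- Directly, in the NEAE summaries by relationship (SAP 10.1).
- Indirectly, through NEAE status of carried-over events (Protocol 11.1, SAP 10.1). As written, a carried-over event with no known pattern can never rise to Possibly Related.
- Not at all, in SAE reporting by sites (Protocol 11.3), the SAE and death outputs (SAP 10.1.2, 10.1.3) and the all-AE tables. The all-NEAE, oral-cavity NEAE and discontinuation tables do not use the rating either, apart from the carried-over route.

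**The case against.** The strongest case on the other side has four parts.

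1. **The pattern condition is broad.** It covers known or expected patterns. The appended insert lists reactions across many body systems, and the Investigator's Brochure may list more. Few events may lack a pattern. This stands as a limit on frequency, but it leaves the definitions incomplete.
2. **Investigators use judgement.** These are descriptions, and a clear drug effect would in practice be rated up to Possibly Related. That is plausible for the second row of the table. It is weaker for unfamiliar events, where the text itself points to a lower rating.
3. **The rating drives little.** No stopping rule, efficacy endpoint or hypothesis test uses it, and sites report SAEs without a causality condition. This stands and sets the size of the point.
4. **A loose rewording could do harm.** If Possibly Related meant only that causality cannot be ruled out, it would overlap with Unlikely Related. With nightly dosing, nearly every event would also meet the timing condition. New wording could also raise the rating of a carried-over event with no clinical change. This stands, and the fix allows for it.

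A reader might infer that new reactions are placed in Unlikely Related by definition and a safety signal would be hidden. The documents do not support that. Unlikely Related needs a reasonable other cause, not merely a conceivable one, and new reactions still appear in the all-NEAE, SAE, discontinuation and oral-cavity tables. Nor can a reader conclude that total NEAE counts are wholly untouched, because an increase in relationship can make a carried-over event newly emergent.

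**Conclusion.** The scale in Protocol 11.2.3 is incomplete, and its highest category is too narrow for a study whose primary objective is safety. Read literally, 2 of the 4 well-timed combinations have no category, and no event without a known or expected pattern can be rated Possibly Related. SAP 7.3.1 imputes a value outside the scale.

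The consequence is confined to the relationship tables and the NEAE status of events ongoing from the lead-in. The number of events affected cannot be derived from the documents, which also do not say which categories would be pooled as drug-related.

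The conclusion assumes that the definitions are applied as written and that no fourth category is missing from the text. The latter seems safe: the list ends on a complete sentence, no redaction is marked, and the contents list puts 11.2.3 and 11.3 on the same page (33). The lead-in's causality scale is not in the documents.

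**What to change.** Keep three categories, and make them exhaustive and non-overlapping.

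- **Possibly Related**: timing is reasonable and there is a reasonable possibility that study drug caused the event, whether or not the pattern is already known and whether or not other factors are present.
- **Unlikely Related**: another cause is clearly more likely than study drug. Absence of a known pattern is no longer a defining condition.
- **Not Related**: keep the beyond-reasonable-doubt standard and make it govern the explanatory text. Otherwise, the clause on another cause being most plausible would overlap with the reworded Unlikely Related. Rating in the order Not, Unlikely, Possibly gives each event one category.

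In SAP 7.3.1, impute a missing relationship to the highest category of this scale. At P303 entry, rate events carried over from the lead-in on the same wording, so that the rewording alone cannot count as an increase in relationship.

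The cost is protocol and CRF-guidance wording, one line in the SAP, and an entry rating for carried-over events. The number of categories and the table layouts stay as they are. Somewhat more events will be rated Possibly Related, and the wording may differ from the lead-in scale, so relationship tables from the two studies may not be directly comparable.

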11.3. Serious Adverse Events (SAEs) and Serious Adverse Drug Reactions

Any SAE that occurs at any time during the study, or within 28 days after the patient’s last exposure to study drug, including a clinically significantly abnormal laboratory test result that is considered serious, must be reported to Tonix or its designee(s) so that Tonix may comply with regulatory obligations. If the SAE is life-threatening or fatal, it must be reported to Tonix or its designee(s) immediately, by email or telephone. For these and all other SAEs, an SAE report form must be completed and sent by facsimile or email to Tonix or its designee(s) within 24 hours of the site’s initial awareness of the event. These requirements apply equally to all patients, regardless of the study phase or the at-risk patient’s treatment assignment.

A serious adverse event (experience) or reaction is any untoward medical occurrence that, at any dose:

[figure not shown]
- Results in death,
- Is life-threatening,
- Requires in-patient hospitalization or prolongation of existing hospitalization,
- Results in persistent or significant disability/incapacity,
- Is a congenital anomaly/birth defect, or
- Is an important medical event

NOTE: The term “life-threatening” in the definition of “serious” refers to an event in which the patient was at risk of death at the time of the event. It does not refer to an event that hypothetically might have caused death if it were more severe.

[figure not shown]
Medical and scientific judgment should be exercised in deciding whether expedited reporting is appropriate in other situations, such as important medical events that may not be immediately life-threatening or result in death or hospitalization but may jeopardize the patient or may require intervention to prevent one of the other outcomes listed in the definition above. *These should also usually be considered serious.* Examples of such events are intensive treatment in an emergency room or at home for allergic bronchospasm, blood dyscrasias or convulsions that do not result in hospitalization, or development of drug dependency or drug abuse.

A death occurring during the study or reported to the Investigator after study participation (no required post-study time limit) must be reported to Tonix or its designee(s) immediately, whether or not it is considered treatment-related. Initial SAE reports must be followed by detailed descriptions. These should include copies of hospital case records and other documents when requested. The CRO will confirm via email or facsimile when it has received SAE documentation. If such confirmation is not received at the site in a timely manner, it is then the responsibility of the site to contact the CRO to ensure that the SAE documentation was indeed received by the CRO.

The Investigator or other study personnel must immediately inform one of the Tonix Medical Monitors by phone or email of any AE considered serious or otherwise significant, as described above. **In addition, a completed SAE report form must be submitted to [REDACTED]
[REDACTED] within 24 hours of the site's initial awareness of the event.**

Contact information for the Medical Monitors is provided below:

For questions pertaining to the reporting of SAEs or the completion of SAE documentation, site personnel should call [REDACTED]

The investigator, or the sponsor or designee in the case of a central Institutional Review Board (IRB), also must notify the EC (Ethics Committee)/IRB of the occurrence of the SAE, in writing, as soon as is practicable and in accordance with local law. A copy of this notification must be provided to Tonix or its designee.

In the event of an SAE that meets the criteria for expedited reporting, an Investigational New Drug (IND) Safety Report will be prepared for submission to the FDA.

